### 12E. Maximum Tolerated Dose for Phase I/IIa anakinra study

The Maximum Tolerated Dose (MTD) will be defined as the highest dose of anakinra studied at which no more than one in six patients experiences a DLT during the 6 weeks of treatment. Subjects will be enrolled at the maximum tolerated dose until a total of 30 subjects have been enrolled in the study. Given the 3+3 design of the study, if there is a DLT then a total of 6 subjects will enrolled per dose level. If we reach the 8 mg/kg/day dose level, then up to a maximum of 12 subjects will be enrolled at a dose level below the MTD (4 mg/kg and 6 mg/kg). This leaves 18 subjects treated at the MTD if the third dosing level is reached. If there are no DLTs at the first two levels, then 3 subjects will be enrolled at the MTD. Thus, between 18 and 24 subjects will be enrolled at the MTD if the 3rd dose level is reached.

### 12F. Stopping Rules

#### 12F1. Stopping rules for Phase I/IIa anakinra study

**Individual stopping rule:** A subject who experiences a DLT will discontinue anakinra immediately and will be monitored for resolution of the toxicity as medically appropriate. All subjects will be monitored for the 6 weeks from the time of enrollment or until resolution of the DLT, whichever is later.

**Study stopping rule:** Table 6 shows the Phase I dose escalation rules. The study will be discontinued if at the first dose (4 mg/kg/day), the number of subjects that experiences a DLT is greater than 2. Otherwise, the study will determine its MTD using the escalation rules described.

# 12F2. Stopping rules for Combination therapy pilot study Individual stopping rules:

A subject who experiences any of the following adverse drug toxicities will discontinue anakinra immediately:

- Serious infection qualifying as an SAE (see Section 13) and requiring intervention
- A decrease in the white blood cell count (WBC) to <1500/mm^3 (Grade 3 severity by NIH/NIAID) (NIH 2009)
- An anaphylactoid reaction to an injection of anakinra

A subject who experiences any of the following adverse drug toxicities will discontinue atorvastatin immediately:

- ALT or AST more than 3x the upper limit of age and sex-adjusted normal AND >50% increase over baseline (pre-IVIG)
- CK elevation > 10 times the upper limit of normal or symptoms of muscle pain due to myositis
- A decrease in total cholesterol (TC) level that is at least 10% lower than entry level AND below 100 mg/dl (~2.5th percentile for children age 2 yrs.)

Any subject who experiences an adverse drug toxicity that warrants discontinuation of a study drug will be monitored for resolution of the toxicity as medically appropriate. All subjects will be monitored for 6 weeks from the time of enrollment or until resolution of the adverse drug toxicity, whichever is later.

**Study stopping rule:** The study will be discontinued if three subjects experience adverse drug toxicities.

# **13. Monitoring Side Effects**

#### 13A. Monitoring side effects for Phase I/IIa anakinra study

Subjects will be monitored for 6 weeks to evaluate for adverse events (AEs). The main side effect of anakinra is an infusion site reaction. The most serious adverse event would be an infection or hypersensitivity reaction. All subjects will be monitored for both AEs and SAEs. An AE is any unfavorable or unintended change in a sign (i.e. abnormal laboratory), symptom or disease temporally associated with the study treatment, whether or not it is considered to be related to the study product.

Table 8: Definition of Adverse Events Associated with Anakinra				
Adverse Event	NOT an Adverse Event (Expected with KD)			
Infusion site reaction	Atopic dermatitis or psoriasis			
Decrease in WBC as per Table 9	Eosinophilia (<35%) or ANC (>500)			
Any infection	Worsening coronary artery dilatation or aneurysm compared to baseline			
	
 
Laboratory values compared to baseline:
 
Worsening anemia
 
Increasing platelet and lymphocyte counts
 
Increasing ESR
 
			

Table 9: Grading Severity of Decrease in WBC Adverse Event (NIH 2009)					
Grade 1 Mild	Grade 2 Moderate	Grade 3 Severe	Grade 4 Potentially Life Threatening		
2,000 – 2,500/mm 	1,500 – 1,999/mm 	1,000 – 1,499/ mm³	< 1,000/mm 		

#### A SAE is defined as any event which:

- 1. Is fatal; or
- 2. Is life-threatening (the patient was, in the view of the Principal Investigator, in immediate danger of death from the event as it occurred); or
- 3. Requires hospital admission or prolongs hospitalization; or
- 4. Is persistent or causing significant disability; or
- 5. Required medical intervention, such as major surgery, to prevent a serious outcome; or
- 6. The Clinical Site Principal Investigator considers it to be a serious adverse event.

SAEs for this trial include, but are not limited to, anaphylaxis, arrhythmia, cardiac arrest, cardiogenic shock, death, hearing loss, hepatitis, hypertension, hypotension, myocardial infarction, renal failure, seizures, sepsis (confirmed), or shock.

Any SAE, independent of causality, which occur in a subject in the Trial, assigned to receive Product will be reported to Sobi. Reports shall be sent to the Sobi Drug Safety Department by email ([contact]), or by fax ([contact]), within 24 hours of first awareness. Similar reporting will occur with the FDA and IRBs as stipulated by their reporting rules. Unanticipated problems in involving risk (UPRs) will be reported to each agency as stipulated by their reporting rules.

#### 13B. Monitoring side effects for Combination therapy pilot study

Subjects will be monitored for 6 weeks to evaluate for AEs. The main side effect of anakinra is an infusion site reaction. The most serious adverse event would be an infection or hypersensitivity reaction. See **Table 8** for definition of AEs associated with anakinra and **Table 9** for grading severity of a decrease in WBC. Subjects will also be monitored for AEs associated with atorvastatin (**Table 10**).

All subjects will be monitored for both AEs and SAEs. An adverse event is any unfavorable or unintended change in a sign (i.e. abnormal laboratory), symptom or disease temporally associated with the study treatment, whether or not it is considered to be related to the study product.

 Table 10: Definition of Adverse Events Associated with Atorvastatin

ALT or AST more than 3x the upper limit of age and sex-adjusted normal AND >50% increase over baseline (pre-IVIG)

CK elevation > 10 times the upper limit of normal or symptoms of muscle pain due to myositis

A decrease in total cholesterol (TC) level that is at least 10% lower than entry level AND below 100 mg/dl (~2.5th percentile for children age 2 yrs.)

A SAE is defined as any event which:

- 1. Is fatal; or
- 2. Is life-threatening (the patient was, in the view of the Principal Investigator, in immediate danger of death from the event as it occurred); or
- 3. Requires hospital admission or prolongs hospitalization; or
- 4. Is persistent or causing significant disability; or
- 5. Required medical intervention, such as major surgery, to prevent a serious outcome; or
- 6. The Clinical Site Principal Investigator considers it to be a serious adverse event.

SAEs for this trial include, but are not limited to, anaphylaxis, arrhythmia, cardiac arrest, cardiogenic shock, death, hearing loss, hepatitis, hypertension, hypotension, myocardial infarction, renal failure, seizures, sepsis (confirmed), or shock.

Any SAE, independent of causality, which occur in a subject in the Trial, assigned to receive Product will be reported to Sobi. Reports shall be sent to the Sobi Drug Safety Department by email ([contact]), or by fax ([contact]), within 24 hours of first awareness. Similar reporting will occur with the FDA and IRBs as stipulated by their reporting rules.

# 14. Additional Therapy for Phase I/IIa anakinra study and Combination therapy pilot study

#### 14a. Management of Treatment-resistant Subjects

Treatment-resistance will be defined as persistent or recrudescent fever ( $T \ge 38.0^{\circ}C$  rectally)  $\ge 36$  hours and <7 days following end of IVIG infusion. Subjects who meet criteria for treatment-resistance will be treated at the Center PI's discretion.

#### 14b. Additional Therapy for Coronary Artery Abnormalities

Additional therapy for coronary artery abnormalities will be at the Center PI's discretion. A Phase III, double-blind, randomized controlled trial of the addition of infliximab to primary treatment with IVIG demonstrated that early treatment of infants and children with acute KD with infliximab plus IVIG had a more rapid decrease in inflammation, fewer days of fever, and a more rapid decrease in the internal

diameter of a dilated coronary artery compared to IVIG therapy alone ([name] 2014). Thus, subjects in this study will be eligible to receive infliximab at the discretion of the Center PI.

# 15. Sample Size

#### 15A. Sample size for Phase I/IIa anakinra study

A study population of a minimum of 18 KD patients treated with the MTD of anakinra (See Section 11E for subjects at MTD) and 18 historic matched controls from the Kawasaki Research database will have 80% power based on a two-sided, paired t-test to compare change scores from baseline between cases and controls with alpha set to 0.05 to detect a minimum difference for the change score for several transcript levels of the IL-1 family, including IL-1RAP (pooled SD of 3.2 and corresponding difference of 2.2) and IL-1R1 (pooled SD of 8 and corresponding difference of 5.6). The effect sizes are based on relevant changes that were found in the largest KD microarray study done to date (Hoang 2014).

#### 15B. Sample size for Combination therapy pilot study

This study is not powered to show a difference in echocardiographic measurements or treatment response compared to controls. Instead, the sample size will be determined based on detectable differences in inflammatory markers and readouts from *in vitro* EC studies. A sample size of 10 KD patients treated with anakinra/atorvastatin combination therapy vs 10 matched historical controls treated with standard therapy alone will have 80% power based on a two-sided, paired t-test with alpha set to 0.05 to detect an effect size of 89% in the mean change of EC homeostasis (i.e. markers of EndoMT) and inflammasome activation (i.e. TIFA, NLRP3) using the *in vitro* EC culture system.

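### Section 15B: 10 pairs give about 71% power, not 80%, under the named paired t-test if the 89% effect means 0.89 SD of the paired differences

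*Combined protocol and SAP*

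**What the plan says.** Section 15B rules out power for echocardiographic measurements and treatment response, and rests the sample size on inflammatory markers and in vitro endothelial-cell (EC) readouts. The comparison is "A sample size of 10 KD patients treated with anakinra/atorvastatin combination therapy vs 10 matched historical controls treated with standard therapy alone". The design "will have 80% power based on a two-sided, paired t-test with alpha set to 0.05 to detect an effect size of 89"%, the effect being a mean change in EC homeostasis and inflammasome activation. It gives no SD, no raw difference, no within-pair correlation and no formula.

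Section 15A, for the Phase I/IIa anakinra study, makes a parallel statement with the same test, alpha and power for 18 cases and 18 matched controls. There the effects are given with their SDs: "IL-1RAP (pooled SD of 3.2 and corresponding difference of 2.2) and IL-1R1 (pooled SD of 8 and corresponding difference of 5.6").

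Section 19B2 plans the paired t-test for continuous outcomes in the pilot, so the test named in 15B is also a planned analysis.

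**The concern.** A paired t-test on 10 pairs has only 9 degrees of freedom, and at that size the normal approximation overstates power noticeably. The 89% in 15B is almost exactly what the normal approximation gives for 10 pairs, whereas the effects in 15A agree with the exact t calculation. That suggests that the 80% in 15B does not belong to the test it names.

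This is the pilot's only power statement. If it is too high, readers of a null result on these readouts will think a miss less likely than it was.

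**Working it through.** **Inputs.** From 15B: 10 pairs, two-sided paired t-test, alpha 0.05, stated power 80%, effect 89%. From 15A: 18 pairs, same test, alpha and power; effects 2.2/3.2 = 0.6875 SD and 5.6/8 = 0.70 SD. Assumption: 89% means d = 0.89 SD of the within-pair differences in change.

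**1. Reproducing the stated 80%.** Normal approximation: power = Φ(d√n − 1.960).
- Φ(0.89 × √10 − 1.960) = Φ(2.814 − 1.960) = 80.4%.
- Detectable effect at 80%: (1.960 + 0.842)/√10 = 0.886, which rounds to 89%.

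The stated figure is therefore reproduced with z in place of t. No formula is named in 15B, so this origin is an inference.

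**2. The test that 15B names.** Noncentral t with df = 9, critical value 2.262, noncentrality 0.89 × √10 = 2.814.
- Power = 70.8%.
- Rounding of the 89% does not explain the gap: 0.885 gives 70.3% and 0.895 gives 71.2%.
- Detectable effect at 80% power with 10 pairs: 0.996 SD.
- Pairs needed for 0.89 SD: 11 give 75.8%, 12 give 80.1%.

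**3. Which unit fits 15A.** Detectable effect at 80% power with 18 pairs:

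| Method | SD units | At SD 3.2 | At SD 8 |
|---|---|---|---|
| Exact paired t | 0.7007 | 2.24 | 5.61 |
| Normal approximation | 0.6603 | 2.11 | 5.28 |
| Published in 15A | | 2.2 | 5.6 |

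Only the exact t, with the quoted SD used as the SD of the paired differences, matches both published values after rounding. Its power is 79.9% at 0.70 SD and 78.5% at 0.6875 SD.

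**4. Between-subject SD units.** If 0.89 is in SDs of the individual change score, the paired effect is 0.89/√(2(1 − ρ)), where ρ is the within-pair correlation. The documents give no ρ, so these values are assumed:

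| ρ | Power, 10 pairs |
|---|---|
| 0 | 43% |
| 0.2 | 51% |
| 0.4 | 63% |
| 0.5 | 71% |
| 0.6 | 80% |
| 0.7 | 90% |

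Power of 80% is reached at ρ = 0.601. At ρ = 0.5 the SD of the differences equals the individual SD, so the two readings coincide: 15A's 0.70 gives 79.9% and 15B's 0.89 gives 70.8%. At ρ = 0.6, 15A's 0.70 would have 87.9% power rather than 80%.

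**5. Other tests.** An unpaired t-test with 10 per group gives 47.0%. A one-sided 0.05 paired t-test gives 82.9%, but 15B specifies two-sided.

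**The case against.** The strongest objection is that 15B never defines the 89%. Taken literally it could be a percent change in the mean, in which case power cannot be computed at all, and 71% is one conditional result. This stands as a limit on certainty about the reading. It does not rescue the 80%, which would then be unsupported.

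The support from 15A is also not unique. A pooled SD normally describes two groups, and 15A's figures fit equally well as a between-subject SD with correlation 0.5. Nor does anything require one correlation for both sections, because 15A concerns transcript levels and 15B concerns cell-culture readouts. A correlation of about 0.60 in 15B alone would give 80%. That is fair, but such a correlation is a necessary input and 15B does not state it. It could also be said that authors who used exact t in 15A would have used it in 15B. The match at 0.886 points the other way without proving it.

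Section 18B lists 20 standard-treatment controls, not 10. With two controls per case, individual-SD units and an assumed correlation of 0.5, power would be 82.4% (75.2% at 0.4). But 15B's claim is explicitly for 10 against 10, so its sentence has to stand on that basis. The difference from 18B should be settled when the sentence is rewritten.

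Finally, this is a 10-patient pilot with safety as its primary outcome (7F2), and its biomarker analyses are not adjusted for multiplicity. The consequence is limited, and no stopping rule or safety decision depends on this figure.

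**Conclusion.** The concern holds. For 10 pairs and the two-sided paired t-test at alpha 0.05, an effect of 0.89 SD of the paired differences has 70.8% power against the stated 80%. If that is the true effect, the chance of missing it is about 29% rather than 20%. The arithmetic is firm. Confidence that 89% means 0.89 SD of the paired differences is moderate, because 15B does not say so.

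Under the other units considered, the sentence is still incomplete: it lacks either a correlation of about 0.60 or an SD. The power sentence itself covers the in vitro EC and inflammasome readouts, which are secondary (7G2). The plasma and whole-blood markers have no power figure of their own. The point should be fixed, but it does not threaten the trial's main purpose.

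**What to change.** In 15B, replace the 89% with an effect in SD units and name the SD. If the SD of the paired differences is meant, a correct statement is: 10 pairs give 80% power to detect a mean within-pair difference in change of 1.0 SD of the paired differences (about 71% for 0.89 SD), two-sided paired t-test, alpha 0.05. If a between-subject SD is meant, state it together with the assumed within-pair correlation (about 0.60 is needed for 80%). If a percent change is meant, give the SD and recompute.

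In the same edit, say whether the standard-therapy comparison uses 10 controls (15B) or 20 (18B), and base the figure on that number.

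The cost is one recalculated sentence and a check of the control count. It needs no extra patients and no design change. The only downside is a slightly less favourable stated figure.

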# 16. Pharmacokinetic Analysis for Phase I/IIa anakinra study

The area under the concentration-time curve (AUC) around the first dose for anakinra will be roughly estimated as the initial concentration (the concentration extrapolated back to time zero) divided by the elimination rate, if the elimination appears first-order (log scale) or zero-order (linear scale). We will also roughly estimate the AUC using the trapezoidal rule up to the last measurable concentration. The extrapolated area after the last concentration will be estimated as  $C_{last/\lambda z}$ , where  $C_{last}$  is the last measurable concentration and  $\lambda z$  is the terminal slope of the curve. AUC from time 0 to infinity AUC0-. S calculated as AUC0-last +  $C_{last/\lambda z}$ . Noncompartmental oral clearance rate (Cl/FNC) is calculated as the ratio of dose to AUC0-. Apparent volume of distribution (Vd/FNC) is calculated as Cl/FNC over  $\lambda z$ . Half-life ( $t_{1/2}$ ) is calculated as 0.693/ $\lambda z$ . Plasma anakinra trough concentrations collected in the subacute phase (weeks 2 and 6) will be compared to the 48 hour post-dose concentration collected during the acute phase (study day 2). AUC0-, Cl/F1-C (oral clearance from 1-compartment model), and Vd/F1-C (volume of distribution from 1-compartment model) will also be determined using a 1-compartment model. This second modeling approach will be used because the data are relatively sparse for an intensive PK study, which may limit our ability to estimate every parameter for some patients.

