## 7G. Secondary Outcomes

#### 7G1. Secondary Outcomes for Phase I/IIa anakinra study

- 1. Pharmacokinetics of anakinra
- 2. Immune-monitoring pre-and post-therapy
  - a. Enumeration of myeloid dendritic cell populations
  - b. Enumeration of activated CD4+ and CD8+ DR+ T cells, enumeration regulatory T cells
- 3. Measures of inflammation pre-and post-therapy
  - a. Transcript abundance changes over time by RNAseq
  - b. Levels of high sensitivity (hs) C-reactive P (CRP), alpha-1 antitrypsin, TNFaR1 and R2, IFNg, IL-1 RAP, IL-1R1 and R2, MMP9, caspase-1, IL-6R, IL-18RAP, IL-12, IL-2, TGFb and IL-10
- 4. Echocardiographic assessment of coronary artery internal diameters expressed as Z scores pre-and post-therapy

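### The Section 16 shortcut for first-dose AUC is also prescribed for zero-order elimination, where it gives a time and not an area

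*Combined protocol and SAP*

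**What the plan says.** The combined protocol and SAP lists "Pharmacokinetics of anakinra" among the secondary outcomes of the Phase I/IIa study (Section 7G1). Section 16 gives three routes to the AUC.

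- **Shortcut.** The first-dose AUC is roughly estimated as C0, the back-extrapolated starting value, "divided by the elimination rate, if the elimination appears first-order (log scale) or zero-order (linear scale"). No separate expression is given for the zero-order case.
- **Trapezoid plus tail.** A second estimate is described as follows: "We will also roughly estimate the AUC using the trapezoidal rule up to the last measurable concentration". To this a tail of Clast/λz is added, and AUC0–∞ is the sum of the two parts. Noncompartmental Cl/F "is calculated as the ratio of dose to" that AUC0–∞. Vd/F is this clearance divided by λz, and half-life is 0.693/λz.
- **Model.** AUC, clearance and volume "will also be determined using a 1-compartment model".

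Section 16 calls λz the terminal slope without saying on which scale it is taken. It does not say which of the AUC estimates will be reported.

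**The concern.** C0 divided by a rate is the standard area under an exponential curve. Under zero-order elimination the curve is a straight line and the rate is in concentration per unit time, so the same division cancels the concentration and leaves hours. An AUC must be concentration × time.

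At stake is the comparability of the shortcut AUCs. If some subjects are judged first-order and others zero-order, their values are in different units and cannot be summarised together or compared across the 4, 6 and 8 mg/kg/day levels. The branch could be reached by chance. Section 11F provides three samples after the initial half-dose (1–3, 4–6 and 7–9 hours), and Section 16 itself describes the data as sparse. With three points, deciding whether the decline is straighter on a log or a linear scale is uncertain.

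**Working it through.** The plan states no concentrations and no AUC, so there is no figure of its own to reproduce. All values of C0, k and k0 below are assumptions for illustration.

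**1. First-order decline.** With C(t) = C0·exp(−k·t) from time zero, the area is C0/k. For C0 = 10 and k = 0.2 per hour, numerical integration gives 50 and the shortcut gives 10/0.2 = 50. For k = 0.5, both give 20. The shortcut is right here.

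**2. Zero-order decline.** With C(t) = C0 − k0·t, the concentration reaches zero at t = C0/k0. The area is a triangle: ½ × C0 × C0/k0 = C0²/(2·k0).

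**3. Units.** C0/k0 is concentration ÷ (concentration/time) = time. C0²/(2·k0) is concentration × time.

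**4. Range.** The true area divided by the shortcut value is C0/2.

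| C0 | k0 (per hour) | Shortcut C0/k0 | Area C0²/(2·k0) | Ratio |
|---|---|---|---|---|
| 1 | 0.1 | 10 | 5 | 0.5 |
| 2 | 0.2 | 10 | 10 | 1 |
| 10 | 1 | 10 | 50 | 5 |
| 10 | 0.5 | 20 | 100 | 5 |
| 1000 | 100 | 10 | 5000 | 500 |

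Four of the five profiles share the same shortcut value because they reach zero at the same time. The ratio also moves with the unit. A profile with C0 = 5 µg/mL and k0 = 0.5 µg/mL per hour gives a shortcut of 10 and an area of 25 µg·h/mL. Written as 5000 and 500 in ng/mL, the same profile still gives 10, while the area is 25,000 ng·h/mL. The ratios in the table show a unit error and do not measure a bias.

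**5. Does the error reach clearance?** Section 16 takes noncompartmental clearance from the trapezoid-plus-tail AUC0–∞, so that route was followed for a linear decline. Assumptions: C0 = 10, k0 = 1 per hour, samples at the window midpoints of 2, 5 and 8 hours, the extrapolated C0 used at time zero, and the linear trapezoidal rule.

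- Concentrations at 0, 2, 5 and 8 hours: 10, 8, 5, 2.
- Trapezoid 0–8 h: 18 + 19.5 + 10.5 = 48.
- Log-scale slope through the three samples: λz = 0.231 per hour.
- Tail: 2/0.231 = 8.66, so AUC0–∞ = 56.7.
- True area: 10²/(2 × 1) = 50. AUC0–∞ is about 13% high, and dose/AUC about 12% low (50/56.7 = 0.88).
- Linear-decline tail: Clast²/(2·k0) = 4/2 = 2, which restores 48 + 2 = 50.

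The stated clearance therefore avoids the shortcut's error. In this example it carries a smaller, separate error, because Clast/λz assumes first-order decline. If λz were instead read from a linear plot, Clast/λz would again be a time. The two agree numerically here (2/1 = 2) only because Clast happens to be 2.

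**The case against.** Four points can be made for the plan.

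- **The estimate is described as rough.** That allows for imprecision but does not cover a result in the wrong units.
- **The brackets may only name the plot from which the rate is read.** This does not help, because the slope of a linear plot is a zero-order rate and the unit mismatch remains.
- **Two other AUC estimates are planned for the same subjects.** This stands and limits the harm. It does not remove the point, since those estimates are additional and Section 16 does not say which one is reported.
- **The branch may never be used.** This also stands. The documents report no concentrations and no expectation of zero-order behaviour, and the half-life and tail formulas are first-order.

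A reader might also infer that Cl/F and Vd/F inherit the shortcut's error. The documents do not support that. Section 16 derives one set from the trapezoid-plus-tail AUC0–∞ and the other from the 1-compartment model, and no parameter is stated to be computed from C0 divided by the rate.

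**Conclusion.** The shortcut is wrong as written for zero-order elimination, and this follows from units alone, whatever the concentrations. The consequence is limited to the shortcut AUC of any subject judged zero-order. How many subjects that would be cannot be told from the documents. No percentage error can be attached to it, because the ratio C0/2 depends on the unit of measurement.

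A reader might take a formula error in a listed secondary outcome as a threat to the trial's conclusions. That would go too far. The primary outcome is safety (Section 7F1), escalation and the MTD rest on counts of dose-limiting toxicities (Sections 12D and 12E), and PK variables are to be summarised descriptively (Section 19A). The point is minor.

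The 12–13% figure for the tail is a related weakness. It rests on one assumed linear profile and assumed sampling times, so it illustrates the issue and does not estimate its size in this trial.

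**What to change.** In Section 16:

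1. Limit C0/k to first-order decline. For zero-order decline, either give AUC = C0²/(2·k0) or delete the clause.
2. State which AUC estimate is the reported one.
3. Define λz as the terminal slope on the log scale.
4. For a subject judged zero-order, use the tail Clast²/(2·k0) and do not report a half-life or Vd/F based on λz. If the zero-order clause is deleted, still say how a profile that looks linear is handled, because the tail, half-life and noncompartmental volume all assume first-order decline.

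The cost is a few sentences in one section. Sampling, data collection and sample size do not change.
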